**ALIVE Study** 

21st January 2022

pending review by the DSMB. This is equivalent to 12 safety events which meet these criteria in 612 subjects recruited at the point of the interim analysis.

Efficacy evaluation: Anti-helminthic primary efficacy, measured by cure rate will be determined by analysing a stool sample taken 21(+/-7) days after completing treatment with Kato Katz, Baermann and PCR. (18,40). Cure is defined as absence of the species of STH in participants who had a positive egg count and/or larva for that STH at baseline. Cure rate (CR) is defined as the proportion of individuals cured (absence of any egg) to the total of those infected at baseline with each particular species of STH.

# Secondary outcome measures

**Treatment efficacy:** Anti-helminthic efficacy, measured through egg reduction rate (ERR), will be determined by analysing a stool sample taken 21(+/-7) days after completing treatment with Kato Katz, Baermann and PCR (40). Egg reduction rate (ERR) will be calculated by using geometric means, calculated for hookworms, *T. trichiura* and *A. lumbricoides*.

At pre- and post-treatment visits a duplicate Kato-Katz test will be performed on a fresh stool sample collected <24 hours before examination. Baermann method will also be performed in parallel to Kato-Katz for the search of *S. stercoralis*. Evaluation by PCR will be performed in pre- and post-treatment samples.

**Pharmacokinetic outcome measures:** Two blood samples for population PK analysis will be collected for every participant by finger prick using the mitra devices (41) in the phase II component to cover the following timepoints to determine FDC concentrations (Cmax), time to reach Cmax (Tmax) and area under the curve (AUC):

- ALB arm: 1, 2, 3, 4, 5, 6, 7, 8, 24h after treatment administration.
- FDC Single dose arm: 1, 2, 3, 4, 5, 6, 7, 8, 24, 48, 72h after treatment administration.
- FDC Three-day arm: 1, 2, 3, 4, 5, 6, 7, 8, 24, 48, 72h after treatment administration (time points considered respective to the last dose on Day 2). In this group, 1 additional timepoint will be collected at Day 2 pre-dose.

Refer to Section 8.2 for additional information on population PK.

Version 4.0 21st January 2022

**ALIVE Study** 

# Participant acceptability/palatability outcome measures:

Facial hedonic scale and implied numerical rating scale (NRS) will be included in the Phase II component of the trial to measure attributes for the FDC orodispersible formulation in terms of taste, aftertaste; mouth feel; smell; time needed to dissolve/disperse (duration of administration). Secondary aspects will include visual aspects: embossing, surface aspects and colour. Refer to Section 9.5.2 for details.

**Resistance:** Whole genome sequencing, next-generation DNA sequencing and omic approaches will be used to assess underlying factors associated with low treatment response including assessment and evaluation of new protocols for sample processing and sequencing.

Version 4.0 21st January 2022

**ALIVE Study** 

4

#### STUDY DESIGN

# 4.1 OVERALL DESIGN

# Study phase and classification

This will be an adaptive phase II/III trial to compare safety and efficacy of the active control arm (current standard of care) against 2 experimental arms.

# **Phase II component**

Uni-centric, 3-arm, parallel, open-label, randomised, phase II trial to determine the safety and tolerability of FDC in paediatric population in different weight strata. Stratification by weight thus recruiting sequentially for safety and tolerability.

- Group 1 (38 participants): with body weight of [23-<30) Kg will receive 300-391  $\mu$ g/Kg (FDC 400mg-9mg) or ALB.
- Group 2 (38 participants): with body weight of [30-45] Kg will receive 400-600 μg/Kg (FDC 400mg-18mg) or ALB.
- Group 3 (50 participants): with body weight of [15-23) Kg will receive 391-600 μg/Kg (FDC 400mg-9mg) or ALB.

[figure not shown]

Figure 2. Phase II design (Kenya)

Version 4.0 21st January 2022

**ALIVE Study** 

A conservative staged approach to weight-groups 1 through 3 will be taken. Enrolment will be sequentially done between weight groups 1 through 3, randomizing for all 3 treatment arms. Once weight group 1 is complete full source document verification of safety data up to Day 7 will be done and data will be shared with the DSMB and reviewed. If the stopping rule is not met, the DSMB will provide clearance to proceed with enrolment to the following weight group.

Once finalized recruitment of weight group 3, if safety data suggest that doses up to 600  $\mu$ g/kg of ivermectin for 3 days are possible, then the DSMB will provide clearance to proceed to the phase III component in order to evaluate safety and efficacy of the FDC when given for 1 or 3 days across the target age/weight range.

# Phase III component

A Single-Blinded, Randomized, Multi-Centre, Parallel-Group, Active-Controlled, Superiority Study to Evaluate the Efficacy and Safety of a Single Day or 3-day Single Dose of FDC for the treatment of *Trichuris trichiura*, hookworm, *Strongyloides stercoralis* in paediatric and young adult population.

- a. Arm 1: Single dose of a tablet of ALB 400 mg (active control arm)
- b. Arm 2: Single dose of a tablet of FDC 400mg-18mg (≥45 kg of body weight at baseline) or 400mg-9mg (<45 kg of body weight at baseline).

- c. Arm 3: Daily dose of a tablet of FDC 400mg-18mg (≥45 kg of body weight at baseline) or 400mg-9mg for 3 days (<45 kg of body weight at baseline).

[figure not shown]

Figure 3. phase III design (Kenya, Ethiopia, Mozambique)

Version 4.0 21st January 2022

ALIVE Study

**Method of Allocation** 

In the phase II component, participants with *T. trichiura* infection (confirmed by Kato-Katz technique in a fresh stool sample) will be enrolled in a sequential manner per weight group in order to administer the desired dose, starting from 300-391  $\mu$ g/kg ivermectin. Participants in the phase II trial will be stratified in different weight groups: Group 1 (23-<30 kg) 38 participants, group 2 (30-45 kg) 38 participants and group 3 (15-23 kg) 50 participants in order to gradually increase the dose of ivermectin in the FDC. Then, participants will be allocated by simple randomization to one of the three study arms (ALB, FDCx1 and FDCx3).

In the phase III component, allocation of participants to study arms will be done by block randomization and stratified by STH species. We will ensure balanced allocation to the three arms in the three study countries. Treatment allocation for each study participant will be concealed in opaque sealed envelopes that will be opened only after enrolment. Study participants will be assigned a unique study number linked to the allocated treatment group. The allocation ratio for the three study arms will be 1:1:1.

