# Phase III Component

A multi-centre, 3-arm, parallel, open-label, randomised, phase III trial to compare **safety and efficacy** of the active control arm (current standard of care) against 2 experimental arms for the treatment of *T. trichiura*, hookworm and *S. stercoralis*, in children and young adult aged between 5-18 years in three sub-Saharan African countries (Ethiopia, Kenya and Mozambique).

Version 4.0

ALIVE Study 21st January 2022

We hypothesise that the FDC of Ivermectin (IVM) and ALB either at single or 3-day regimens will be more effective against some species of Soil Transmitted Helminths (STH) (*T. trichiura,* hookworm and *S. stercoralis*) compared to the current use of a single dose regimen of 400mg ALB.

Estimated sample size: 1097 participants

Participants will be randomly allocated with unequal probability, according to the specific expected cure rate by treatment and specie, to one of the three study treatment arms:

**Treatment Arm 1:** Single dose of a tablet of ALB 400 mg (active control arm).

**Treatment Arm 2:** Single dose of a tablet of FDC 400mg-18mg or 400mg-9mg.

- For participants <45 kg of body weight at baseline: FDC of 400mg ALB- 9mg IVM.
- For participants ≥45 kg of body weight at baseline: FDC of 400mg ALB-18mg IVM.

**Treatment Arm 3:** Daily dose of a tablet of FDC 400mg-18mg or 400mg-9mg for 3 days.

- For participants <45 kg of body weight at baseline: FDC of 400mg ALB-9mg IVM.
- For participants ≥45 kg of body weight at baseline: FDC of 400mg ALB- 18mg IVM.

In the phase III component, allocation of participants to study arms will be done by block randomization and stratified by the species of STH. Treatment allocation for each study participant will be concealed in opaque sealed envelope that will be opened only after enrolment. Study participants will be assigned a unique number linked to the allocated treatment group.

Version 4.0

ALIVE Study 21st January 2022

The phase II and III trial components comprise of a screening phase, an enrolment phase, a treatment phase, a post-treatment phase with follow-up visits, and early withdrawal/end-of-study evaluations.

Participants recruited in Mozambique will be offered to be tested for HIV serostatus due to the high HIV prevalence in the country, but the result will not determine the participant's eligibility. In Kenya and Ethiopia, the low HIV prevalence does not justify HIV testing.

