# Phase III Component

Participants will be randomly allocated with unequal probability, according to the specific expected cure rate by specie, to receive either:

**Treatment Arm 1**: Single dose of a tablet of ALB 400 mg (active control arm).

Treatment Arm 2: Single dose of a tablet of FDC 400mg-18mg or 400mg-9mg.

- o For participants <45 kg of body weight at baseline: FDC of 400mg ALB-9mg IVM.
- o For participants ≥45 kg of body weight at baseline: FDC of 400mg ALB-18mg IVM.

Treatment Arm 3: Daily dose of a tablet of FDC 400mg-18mg or 400mg-9mg for 3 days.

- o For participants <45 kg of body weight at baseline: FDC of 400mg ALB-9mg IVM.
- o For participants ≥45 kg of body weight at baseline: FDC of 400mg ALB-18mg IVM.

FDC will be provided as an oral dispersible formulation, while ALB will be a chewable pill. Both FDC and ALB will be taken with water after a light meal, followed by visual observation of the participant by the study physician at each site. Vomiting 1h post-treatment will require re-dosing. The participants will not

Version 4.0

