**ALIVE Study** 

Table 2. Final sample size calculation taking into account 10% lost-to-follow-up

	Pha	ase II		PHASE III	PHASE II/III
		N total		N total	
		Phase		Phase	
Group	N	ll 	N	III 	N total
Trichuris trichiura					
ALB	23	26	93	103	129
FDCx1	45	50	178	198	248
FDCx3	45	50	178	198	248
Total	113	126	449	499	625
Strongyloides.					
stercoralis					
ALB			42	47	47
FDCx1			108	120	120
FDCx3			107	119	119
Total		0	257	286	286
Hookworm					
ALB			91	101	101
FDCx1			91	101	101
FDCx3			99	110	110
Total		0	281	312	312
TOTAL		126		1097	1223

<sup>1Calculated by inflating the sample size using considering 10% lost-to-follow-up

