3.3 Treatment

Phase II component

Participants will be randomly allocated with unequal probability to receive either:

Treatment Arm 1: Single dose of a tablet of ALB

Treatment Arm 2: Single dose of a tablet of FDC

Treatment Arm 3: Daily dose of a tablet of FDC for 3 days.

and will be recruited by μ g/Kg of IVM to be received in a sequential manner starting from Group 1 through to Group 3 as shown below:

- Group 1: receiving 300-391 μg/Kg or ALB 400mg- 38 participants (body weight: 23-<30 Kg) will be recruited in this group. (FDC 400mg-9mg).
- Group 2: receiving 400-600 µg/Kg or ALB 400mg− 38 participants (body weight: 30-45 Kg) will be recruited in this group. (Participants <45 kg: FDC of 400mg ALB-9mg IVM, participants ≥45 kg: FDC of 400mg ALB-18mg IVM).
- Group 3: receiving 391-600 μg/Kg or ALB 400mg- 50 participants (body weight: 15-23 Kg) will be recruited in this group. (FDC 400mg-9mg).

Phase III Component

Participants will be randomly allocated with unequal probability (Arm 1 p=0.2, Arm2 p=0.4, Arm3 p=0.4), according to the specific expected cure rate by specie, to receive either:

Treatment Arm 1: Single dose of a tablet of ALB 400 mg (active control arm).

- Treatment Arm 2: Single dose of a tablet of FDC 400mg-18mg or 400mg-9mg.
 - For participants <45 kg of body weight at baseline: FDC of 400mg ALB-9mg IVM.

◦ For participants ≥45 kg of body weight at baseline: FDC of 400mg ALB-18mg IVM.

Treatment Arm 3: Daily dose of a tablet of FDC 400mg-18mg or 400mg-9mg for 3 days.

- For participants <45 kg of body weight at baseline: FDC of 400mg ALB-9mg IVM.
- For participants ≥45 kg of body weight at baseline: FDC of 400mg ALB-18mg IVM.

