3.4 Randomisation

In the phase II component, participants with *T. trichiura* infection (confirmed by Kato-Katz technique in a fresh stool sample) will be enrolled in a sequential manner per weight group in order to administer the desired dose, starting from 300-391 μ g/kg ivermectin. Participants in the phase II trial will be stratified in different weight groups: Group 1 (23-<30 kg) 38 participants, group 2 (30-45 kg) 38 participants and group 3 (15-23 kg) 50 participants in order to gradually increase the dose of ivermectin in the FDC. Then, participants will be allocated by simple randomization to one of the three study arms with unequal probability (ALB: p=0.2, n=26; FDCx1: p=0.4, n=50; FDCx3: p=0.4, n=50) In the phase III component, allocation of participants to study arms will be done by block randomization and stratified by STH species. We will ensure balanced allocation to the three arms in the three study countries. Treatment allocation for each study participant will be concealed in opaque sealed envelopes that will be opened only after enrolment. Study participants will be assigned a unique study number linked to the allocated treatment group. Participants will be randomly allocated with unequal probability, according to the specific expected cure rate of each species.

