3.6 Study stopping guidance

The following stopping rules will apply at relevant key instances in the ALIVE study:

- **ISGIODAI** Barcelona Institute for Global Health
 - The occurrence of ≥1 serious adverse reaction (where causality is at least possible) or SUSAR in any of the weight groups in the Phase II will result in suspension of dose escalation in the FDC arm pending review by the DSMB (keeping in mind the sequential recruitment strategy in phase II).
 - 2. The occurrence of ≥2 serious adverse reactions or SUSARs at the end of phase II will result in suspension of progress to phase III pending review by the DSMB.

Overall the occurrence of serious adverse reactions or suspected unexpected serious adverse reactions in 2% of the study populations at interim analysis (50% recruitment) will result in suspension of further dosing of the Investigational Product pending review by the DSMB. This is equivalent to 12 safety events which meet these criteria in 612 participants recruited at the point of the interim analysis.

Table 3. Sample size and power calculation according to the expected efficacy (Cure Rate) of the different treatment arms

Comparison Trichuris trichiura	Target Power	Actual Power	Sample Size	Expected Cure Rate	Overall Alpha	Bonferroni adjusted Alpha
ALB vs IVM-ALB vs (IVM-ALB)x3 IVM-ALB vs (IVM-ALB)x3	80% 80% 80%	91% 100% 80%	116 223 223	23.7% 43.7% 59%	0.05 0.05 0.05	0.0167 0.0167 0.0167
Strongyloides stercoralis ALB vs IVM-ALB vs (IVM-ALB)x3	80% 80%	95% 100%	42 108 107	45% 79% 94%	0.05 0.05	0.0167 0.0167
IVM-ALB vs (IVM-ALB)x3 Hookworm ALB vs IVM-ALB vs (IVM-ALB)x3 IVM-ALB vs (IVM-ALB)x3	80% 80% 80% 80%	80% 82% 80%	91 91 99	79.5% 79.5% 95%	0.05 0.05 0.05 0.05	0.0167 0.0167 0.0167 0.0167

	Pł	nase II		PHASE III		PHASE II/III
		N total			N tota	al
		Phase			Phase	
Group	N	II ¹	Ν		III ¹	N total
Trichuris trichiura						
ALB	23	26	93		103	129
FDCx1	45	50	178		198	248
FDCx3	45	50	178		198	248
Total	113	126	449		499	625
Strongyloides.						
stercoralis						
ALB			42		47	47
FDCx1			108		120	120
FDCx3			107		119	119
Total		0	257		286	286
Hookworm						
ALB			91		101	101
FDCx1			91		101	101
FDCx3			99		110	110
Total		0	281		312	312
TOTAL		126			1097	1223

Table 4. Final sample size calculation taking into account 10% lost-to-follow-up

¹Calculated by inflating the sample size using considering 10% lost-to-follow-up

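### Phase III allocation is given in three incompatible ways (1:1:1, a single 0.2/0.4/0.4, and species-specific ratios), and the stated powers assume only the last

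*Protocol*

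**What the plan says.** Three Phase III rules stand in the current text.

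- **Equal.** Protocol 4.1, Method of Allocation: "The allocation ratio for the three study arms will be 1:1:1".
- **One unequal ratio for all species.** SAP 3.3: "unequal probability (Arm 1 p=0.2, Arm2 p=0.4, Arm3 p=0.4), according to the specific expected cure rate by specie".
- **Unequal, differing by species.** In words, the protocol synopsis ("unequal probability, according to the specific expected cure rate by treatment and specie"), protocol 6.1.2 ("Participants will be randomly allocated with unequal probability, according to the specific expected cure rate by specie, to receive either") and SAP 3.4 ("Participants will be randomly allocated with unequal probability, according to the specific expected cure rate of each species"). In numbers, protocol Table 2 and SAP Table 4 (ALB/FDC/FDCx3): *T. trichiura* 103/198/198, *S. stercoralis* 47/120/119, hookworm 101/101/110.

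Protocol 4.1 also states "We will ensure balanced allocation to the three arms in the three study countries". SAP 3.4 repeats that sentence, and protocol 6.3 says much the same of the sites.

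Protocol 4.2 counts a child with a mixed infection towards each species. Protocol 6.3 says such a child is allocated in the same way as one with a single infection. Neither section says in which species stratum.

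**The concern.** A ratio cannot be both 1:1:1 and unequal. A single 0.2/0.4/0.4 also cannot reproduce the hookworm rows of the SAP's own Table 4, where ALB has about a third of the places. A reader cannot tell which rule produced the randomisation list.

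The powers in protocol 9.2 and SAP 3.5 are true only for the allocation they assume. If the list followed another rule, some of them are misstated. The contrast most exposed is FDC vs FDCx3. It is not among the specific hypotheses in protocol 9.1, but it is sized at 80%, and both documents use a 15-point gain over single-dose FDC to decide whether the 3-day regimen is worth considering.

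The unnamed stratum matters because the table ratios differ. A child with *T. trichiura* and hookworm has a 0.21 chance of ALB in one stratum and 0.32 in the other.

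**Working it through.** **Inputs.** From protocol 9.2, Tables 1 and 2 (SAP Tables 3 and 4):
- Cure rates ALB/FDC/FDCx3: *T. trichiura* 23.7/43.7/59%, *S. stercoralis* 45/79/94%, hookworm 79.5/79.5/95%.
- Evaluable numbers: 116/223/223, 42/108/107 and 91/91/99.
- Two-sided alpha 0.05/3 = 0.0167 per comparison, so z = 2.394.

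**Shares implied by the tables.** *T. trichiura* 103/499, 198/499, 198/499 = 0.21/0.40/0.40. *S. stercoralis* 47/286, 120/286, 119/286 = 0.16/0.42/0.42. Hookworm 101/312, 101/312, 110/312 = 0.32/0.32/0.35.

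**ALB places in Phase III.** Table: 103 + 47 + 101 = 251. Equal: 1097/3 = 366. Flat 0.2: 0.2 × 1097 = 219. Headcounts are lower if children are co-infected, since each counts once per species.

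**Formula.** Pooled normal approximation: power = Φ[(|p1 − p2| − z·s0)/s1], with s0 = √[p̄(1 − p̄)(1/n1 + 1/n2)], p̄ the pooled rate, and s1 = √[p1(1 − p1)/n1 + p2(1 − p2)/n2].

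**The plan's own figure first.** *T. trichiura*, FDC vs FDCx3, 223 per arm: p̄ = 0.5135, s0 = 0.0473, s1 = 0.0468. (0.153 − 2.394 × 0.0473)/0.0468 = 0.85, so power is 80.2% (stated 80%).

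**Same comparison under 1:1:1.** If only Phase III is 1:1:1, each arm gains 449/3 ≈ 150, giving 23 + 150 = 173 and 45 + 150 = 195 in each FDC arm. Then s0 = 0.0506, s1 = 0.0500, (0.153 − 2.394 × 0.0506)/0.0500 = 0.64, and power is 73.8%. With both phases 1:1:1 (187 per arm) it is 71.7%.

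**All comparisons.** Each species' evaluable total is held fixed and redistributed. Entries are pooled-approximation power, with exact binomial enumeration of the same test in brackets.

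| Comparison | Stated | Table ratios | 1:1:1 | 0.2/0.4/0.4 |
|---|---|---|---|---|
| *T. trichiura* ALB vs FDC | 91% | 90.6 (90.7) | 95.5–95.9 (95.5–95.9) | 89.9 (90.0) |
| *T. trichiura* ALB vs FDCx3 | 100% | 100 | 100 | 100 |
| *T. trichiura* FDC vs FDCx3 | 80% | 80.2 (79.6) | 71.7–73.8 (70.6–74.2) | 80.6 (80.3) |
| *S. stercoralis* ALB vs FDC | 95% | 94.7 (95.0) | 99.1 (99.0) | 96.8 (96.8) |
| *S. stercoralis* ALB vs FDCx3 | 100% | 100 | 100 | 100 |
| *S. stercoralis* FDC vs FDCx3 | 80% | 80.0 (82.9) | 69.0 (70.6) | 78.1 (80.3) |
| Hookworm ALB vs FDCx3 | 82% | 80.1 (82.9) | 79.2 (81.7) | 73.7 (76.0) |
| Hookworm FDC vs FDCx3 | 80% | 80.1 (82.9) | 79.2 (81.7) | 86.7 (89.3) |

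Evaluable numbers: 1:1:1 uses 173/195/195 or 187 each (*T. trichiura*), 86 each and 94 each; 0.2/0.4/0.4 uses 112/225/225, 51/103/103 and 56/112/112.

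**At an unadjusted 0.05,** which SAP 5.4.4 implies by dropping multiplicity adjustment, the three affected comparisons become 84–86% (*T. trichiura* FDC vs FDCx3, 1:1:1), 83% (*S. stercoralis* FDC vs FDCx3, 1:1:1) and 84% (hookworm ALB vs FDCx3, 0.2/0.4/0.4).

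**Slips in the same text,** which carry no weight in the conclusion:
- FDC sums to 198 + 120 + 101 = 419 and FDCx3 to 198 + 119 + 110 = 427. Protocol 9.2 and SAP 3.5 print these the other way round.
- The two hookworm comparisons have identical inputs (91 at 79.5%, 99 at 95%) but are given 82% and 80%.
- Protocol 6.1.2 says Phase II allocation is equal, whereas the synopsis and SAP 3.4 give 0.2/0.4/0.4.

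**The case against.** The strongest reply is that the intended rule is clear from the weight of the text. The synopsis, protocol 6.1.2, SAP 3.4, both tables and the stated 251 ALB participants all point to species-specific unequal allocation. SAP 3.4 repeats the protocol 4.1 paragraph but closes with unequal probability by species where 1:1:1 stood. For *T. trichiura*, 0.2/0.4/0.4 is practically the table ratio, so the primary species has one outlying sentence. The balanced-allocation wording can mean no more than keeping the ratio at each site. Power against ALB is safe, and under the SAP's unadjusted 0.05 none of the affected comparisons falls below 80%.

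Much of this stands. The 1:1:1 sentence may well be leftover wording, and the practical consequence is limited. The table ratios' match to the stated powers is also what one would expect, since those powers were evidently calculated from those numbers. It shows which allocation the power statement assumes, not which list was used. The 2-point agreement holds for the pooled approximation; by exact enumeration two table-ratio powers sit 2.9 points above the stated value.

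The reply does not remove the contradiction. The 1:1:1 sentence is in protocol version 4.0, in the paragraph that defines allocation. Deleting it would still leave SAP 3.3 at odds with SAP Table 4 for hookworm (0.2 against 0.32 on ALB) and, less so, for *S. stercoralis*. The powers are stated at 0.0167, whatever alpha the analysis uses. The co-infection stratum stays unnamed on any reading.

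**Conclusion.** The concern holds, as a matter that should be corrected rather than a threat to the primary result. Phase III allocation is specified in three ways that cannot all be true.

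If the list did not follow the tables, the misstated powers at 0.0167 are FDC vs FDCx3 under 1:1:1 (6 to 8 points low for *T. trichiura*, 11 for *S. stercoralis*) and hookworm ALB vs FDCx3 under 0.2/0.4/0.4 (8 points low). Two differences are too small to count as shortfalls: *S. stercoralis* FDC vs FDCx3 under 0.2/0.4/0.4, and hookworm under 1:1:1. *T. trichiura* power against ALB is about 90% or more under every scheme.

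These figures assume the plan's cure rates and 10% loss, species totals held fixed, and no gain in numbers from co-infection. The documents do not show which ratio was used.

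**What to change.** - State the ratio actually used for the randomisation list identically in protocol 1.1, 4.1, 6.1.2 and 6.3 and in SAP 3.3 and 3.4.
- If the list follows Table 2, delete the 1:1:1 sentence and the single 0.2/0.4/0.4 for Phase III, and reword the balanced-allocation sentences as the same species-specific ratio at each site.
- If it does not, recompute the power table for the ratio used, with its alpha. Do not enrol more participants to compensate.
- Name the stratum, and hence the ratio, in which a co-infected child is randomised.
- Correct the arm totals to 419 FDC and 427 FDCx3, give the two hookworm comparisons one power (80% by the formula that matches the other stated powers), and reconcile the Phase II wording.

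The cost is a wording amendment to the protocol, which under protocol 10.1 needs IRB/EC approval before it is implemented, and a SAP revision, plus a recomputed power table if the list departs from Table 2. There are no extra participants, visits or tests.
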